7 DOSING DELAYS/DOSING MODIFICATIONS

7.1 Recording Dose Modifications

All dosing interruptions and modifications will be recorded in the source documents and captured in the OnCore database.

7.2 Toxicity Assessment

Dose reduction should be limited to management of toxicity related to study treatment and not for management of side effects determined by the investigator to be related to underlying disease or other medical condition or concomitant treatment.

If a patient experiences more than one toxicity:

- Dose reduction should be according to the instructions for the toxicity with the higher(est) grade.
- In the case of 2 or more toxicities of the same grade, the investigator may dose reduce according to the toxicity determined to be the most likely to be related to study treatment.

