7.5.2 Dose Modification Instructions for AR-42

In addition to the general dose modification instructions provided in Section 7.4, and the dose reduction steps listed on the table above, dose modification instructions for specific toxicities related to AR-42 are listed in Table 5.

Note: Some pazopanib-related toxicities may result in medical reasons to also hold, omit, or discontinue AR-42. When AR-42 modification/discontinuation is also required, the pazopanib dose modification tables (Table 7, Table 8, Table 9, and Table 10) will also specify the required AR-42 modification.

Grade (CTCAE v4.0)	AR-42 Modification (Refer to Table 4 for AR-42 dose reduction steps)
Blood and Lymphatic System Disorders	
Grade 3 or 4 anemia	Hold/omit ^A AR-42 until resolution to ≤ grade 2; transfusions are permitted.
Grade 3 or 4 febrile neutropenia	Hold/omit ^A until resolved; reduce dose by one dose reduction step when resuming treatment. ^B
Infections and Infestations	
Grade 3 infection	Hold/omit ^A until recovered to ≤ grade 2; at the investigator's discretion, the dose may be reduced by one dose reduction step when resuming treatment. ^B
Grade 4 infection	Hold/omit ^A until recovered to ≤ grade 2; reduce dose by one dose reduction step when resuming treatment. At the investigator's discretion, study treatment may be discontinued.
Investigations	
Grade 3 or 4 ECG QTc interval prolonged	Refer to Table 7 for instructions.
Grade 3 neutrophil count decreased; required ≤ 7 days for recovery to ≤ grade 2	Hold/omit ^A until ≤ grade 2. Dose reduction is not required when resuming treatment.
Grade 3 neutrophil count decreased; > 7 days required for recovery to \leq grade 2	Hold/omit ^A until ≤ grade 2; reduce dose by one dose reduction step when resuming treatment.
Grade 4 neutrophil count decreased	
Grade 3 platelet count decreased; ≤ 7 days required for recovery to ≤ grade 2	Hold/omit ^A until ≤ grade 2. Dose reduction is not required when resuming treatment.
Grade 3 platelet count decreased; > 7 days required for recovery to ≤ grade 2 Grade 4 platelet count decreased	Hold/omit [▲] until ≤ grade 2; reduce dose by one dose reduction step when resuming treatment.
Nervous System Disorders	
Grade 2 pre-syncope or grade 3 syncope (potentially reflecting cardiotoxicity)	Refer to Table 7 for instructions.
Other Toxicities Possibly Related to AR-42	(see footnote c)

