7.7 Pazopanib Dose Modification Instructions

In addition to the general dose modification instructions provided in Section 7.4, dose modification instructions for pazopanib-related toxicities are listed in Table 7, Table 8 (liver function abnormalities), Table 9 (PPE), and Table 10 (Other).

Note: For some toxicities, AR-42 instructions are also included on the tables listed above.

Toxicity	Pazopanib Modification			
	(Refer to Table 6 for pazopanib dose reduction steps)			
Cardiac	Hold/omit ^A pazopanib and determine LVEF.			
Grade 2 heart failure	 If < 15% absolute decline in LVEF compared with baseline or a decline in LVEF of < 10% compared with baseline and ≥ 50%: When symptoms of heart failure show clinical improvement, resume pazopanib with reduction in dose of one dose reduction step.^B If ≥ 15% absolute decline in LVEF compared with baseline or a decline in LVEF of ≥ 10% compared with baseline and < 50%: Continue holding until clinical improvement in symptoms and until LVEF improves to within 10% of baseline. Refer patient for cardiology consult. Reduce pazopanib dose by one dose reduction step when resuming treatment.^B At investigator's discretion, pazopanib may be discontinued. 			
Grade 3 or 4 heart failure	Discontinue pazopanib (also discontinue AR-42).			
Grade 3 or 4 MI	Discontinue pazopanib (also discontinue AR-42).			
Endocrine Disorders				
Grade 2 hypothyroidism	Continue pazopanib (dose reduction not required); initiate hypothyroidism management.			
Grade 3 or 4 hypothyroidism	Discontinue pazopanib; initiate/continue hypothyroidism management.			
Gastrointestinal Disorders				
≥ Grade 1 fistula	Discontinue pazopanib (also discontinue AR-42).			
≥ Grade 2 perforation				
Investigations				

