Grade 3 ECG QTc interval prolonged See Section 6.8 for additional instructions regarding QT monitoring.	 Hold/omit^A pazopanib and AR-42. Check potassium, magnesium, and calcium levels; immediately administer potassium, magnesium, and/or calcium to achieve potassium level of ≥ 4 mEq, magnesium level of ≥ 2 mEq, and calcium WNL. Consider chronic supplementation for maintenance of electrolytes. Review with investigator prior to patient's next scheduled treatment, considering the following: Hold pazopanib and AR-42 until QTc recovers to pre-study treatment baseline (≤ grade 1 [≤ 480ms]). When QTc returns to baseline, resume pazopanib and AR-42 with additional QTc monitoring at earliest opportunity within 8 days after resuming study treatment. If QTc prolongation is thought to be related to pazopanib, decrease pazopanib and AR-42 doses by one dose reduction step when resuming study treatment. For recurrent grade 3 QTc thought to be related to pazopanib and AR-42. 			
Grade 4 ECG QTc interval prolonged	Discontinue pazopanib (also discontinue AR-42).			
Elevation in AST, ALT, and/or bilirubin	Refer to Table 8 .			

Table 7.	Pazopanib	Dose	Modification	Instructions
	i uzopullio	0000	mounounon	in ou douono

 ≥ Grade 2 Reversible Posterior Leukoencephalopathy Syndrome (RPLS) Grade 2 pre-syncope or grade 3 syncope (potentially reflecting cardiotoxicity) 	 An evaluation for RPLS should be performed if the patient presents with seizures, headache (in conjunction with other RPLS symptoms), visual disturbances, confusion, or altered mental function. If RPLS is diagnosed, discontinue pazopanib (also discontinue AR-42). Hold/omit^A pazopanib and AR-42. Obtain 12-lead ECG for cardiology review/consultation. Check potassium, magnesium, and calcium levels; immediately administer potassium, magnesium, and/or calcium to achieve potassium level of ≥ 4 mEq, magnesium level of ≥ 2 mEq, and calcium WNL. If ECG shows new dysrhythmia or QTc ≥ grade 2 (> 480ms), hospitalize for monitoring with cardiology consultation. Hold pazopanib and AR-42 until any potassium, magnesium, and

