	 calcium abnormalities are corrected, symptoms resolved, and QTc improved to ≤ grade 1 (≤ 480ms). Reintroduce pazopanib and AR-42 with input from cardiology and with additional QTc evaluation, either concurrent with reintroduction or at earliest possible opportunity within 8 days from reintroduction. If event is thought to be related to study treatment, reduce the dose of pazopanib and AR-42 by one dose reduction step when resuming study treatment.^B Consider chronic supplementation for maintenance of electrolytes. For recurrent syncope or near-syncope thought to be related to study treatment, consider discontinuation of both pazopanib and AR-42.
Renal and Urinary Disorders	
≥ Grade 2 proteinuria	 Hold/omit^A pazopanib. If assessment of proteinuria was based on a urine dipstick reading, a 24-hour urine collection is required. Based on the 24-hour urine specimen: If grade 2 proteinuria, consult nephrology. If urine protein is < 3.0 gm/24 hours, study treatment may be continued without dose modification pending nephrology consult. If ≥ 3.0 gm/24 hours, hold study treatment until improvement to < 3.0 gm/24 hours or additional nephrology recommendations. If grade 3 proteinuria, consult nephrology and discontinue pazopanib.
Respiratory, Thoracic, and M	ediastinal Disorders
≥ Grade 2 pneumonitis	Discontinue pazopanib (also discontinue AR-42).
Skin and Subcutaneous Disc	rders
PPE (hand-foot syndrome)	See Table 9 for instructions related to PPE

Table 7. Pazopanib Dose Modification Instructions (continued)

Table 7. Pazopanib Dose Modification Instructions (continued)

Tuble III azopanie Beee mea	
Vascular Disorders	
Grade 3 hypertension defined as systolic BP >160 mmHg and diastolic BP >100 mm/Hg	 Hold/omit^A pazopanib until resolution to ≤ grade 2. Administer standard antihypertensive therapy. When resuming pazopanib, decrease pazopanib dose by one dose reduction step; monitor BP weekly for 4 weeks. If BP remains controlled for at least one cycle, the pazopanib dose may be escalated by one dose step at the investigator's discretion.
Grade 4 hypertension	Discontinue pazopanib (also discontinue AR-42)
	an the first 4 weeks of the cycle, any remaining doses for that cycle are 7.4 for additional information.

B. At the investigator's discretion (after the DLT evaluation period [Section 6.7.1]), the dose may be escalated by one dose step when the toxicity has resolved and treatment can be resumed.

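### Section 7.2 ties the dose reduction to the highest-grade toxicity, but for AR-42 three grade 3–4 rows carry no reduction while two grade 2 rows do

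*Combined protocol and SAP*

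**What the plan says.** Section 7.2 ranks concurrent toxicities by grade: "Dose reduction should be according to the instructions for the toxicity with the higher(est) grade". For toxicities of equal grade, "the investigator may dose reduce according to the toxicity determined to be the most likely to be related to study treatment". Neither sentence says that the stricter instruction prevails, and neither says that the rule is applied separately to AR-42 and pazopanib.

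The dose instructions themselves are in Section 7.5.2 (Table 5, AR-42) and Section 7.7 (Tables 7–10, pazopanib, with AR-42 actions where needed).

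- Table 5, grade 3 neutrophil decrease and grade 3 platelet decrease, each recovering within 7 days: AR-42 is held, and "Dose reduction is not required when resuming treatment".
- Table 5, grade 3 or 4 anemia: hold or omit "AR-42 until resolution to ≤ grade 2; transfusions are permitted". No reduction step is given.
- Table 7, grade 2 pre-syncope: both drugs are held and, if the event is thought related to study treatment, both resume one step lower. Table 5 lists this event as well and refers to Table 7.
- Table 8, grade 2 ALT/AST with bilirubin above 2 × ULN: both drugs are held and, if treatment is restarted, both are reduced by one step.
- Table 7, grade 2 heart failure: "When symptoms of heart failure show clinical improvement, resume pazopanib with reduction in dose of one dose reduction step".
- Table 9, grade 2 PPE that interferes with instrumental ADL: pazopanib is reduced by one step.

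**The concern.** A rule that lets the highest grade decide is safe only if the reductions get stricter, or at least no milder, as grade rises. Here some grade 3–4 events carry no reduction and some grade 2 events carry one. When two such events coincide, following Section 7.2 literally removes a reduction that another table calls for. Two investigators, each following a written instruction, could resume the same patient at different doses.

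The first thing at stake is the patient's dose. There is also an indirect link to the trial's result. Section 6.7.4 allows an RP2D below the MTD in view of overall tolerability, including how often doses were modified, and Section 13.3 summarises dose modification under the primary objective. That information would depend partly on which instruction was followed.

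**Working it through.** The plan gives no figure to reproduce, so the check sets table rows against the Section 7.2 rule.

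**Step 1. Higher-grade rows with no AR-42 reduction (Table 5).** There are three: grade 3 neutrophils recovering in ≤ 7 days, grade 3 platelets recovering in ≤ 7 days, and grade 3 or 4 anemia.

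**Step 2. Grade 2 rows with a mandatory or conditional one-step reduction.**

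| Grade 2 row | AR-42 | Pazopanib |
|---|---|---|
| Pre-syncope, thought treatment-related (Table 7) | one step | one step |
| ALT/AST with bilirubin elevation, on restart (Table 8) | one step | one step |
| Heart failure (Table 7) | none stated | one step |
| PPE interfering with instrumental ADL (Table 9) | none stated | one step |

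**Step 3. Apply Section 7.2 drug by drug.** Table 5 sets only the AR-42 dose, so its three rows cannot override a pazopanib instruction. The heart failure and PPE rows drop out. The two rows that reduce AR-42 remain:

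3 × 2 = 6 row pairs in conflict, all on the AR-42 dose.

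**Step 4. Apply Section 7.2 to the regimen as a whole.** The highest-grade row then governs both drugs, and all four grade 2 rows are affected:

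3 × 4 = 12 row pairs in conflict. Six are those of Step 3, now with pazopanib affected as well; the other 12 − 6 = 6 involve pazopanib only.

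**Step 5. What one pair means for a patient.** Suppose a patient who started at 30 mg AR-42 and 800 mg pazopanib (dose level 3A) has a grade 3 neutrophil decrease that recovers in 5 days, together with related grade 2 pre-syncope. Section 7.2 points to the neutrophil row, so AR-42 resumes at 30 mg. Table 7 with Table 4 gives 20 mg. The difference is (30 − 20)/30 = 33% of the AR-42 dose. One Table 4 step is 10/40 = 25% from 40 mg and 10/20 = 50% from 20 mg; from 10 mg it is discontinuation of AR-42. If Section 7.2 is not applied per drug, pazopanib also differs: 800 mg against 600 mg in Table 6.

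**The case against.** The strongest reply is that the protocol is organised by drug. Tables 4 and 6 are separate reduction ladders. Section 7.4 keeps one drug going while the other is interrupted, unless the instructions say otherwise. The note in Section 7.5.2 says the pazopanib tables will specify any AR-42 change that is also needed. This supports a per-drug reading, although Section 7.2 does not state it. On that reading, a short grade 3 neutropenia with grade 2 heart failure is no contradiction: one row sets AR-42, the other sets pazopanib, and both can be followed. The same holds for PPE. That part of the objection stands, and it reduces the count from 12 to 6. It does not remove the six, because there both instructions concern AR-42.

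A reader might go further and infer that Section 7.2 can override the rows that stop both drugs at low grade, such as "≥ Grade 1 fistula" and "≥ Grade 2 pneumonitis". The documents do not support that. Section 7.2 concerns dose reduction only, and Section 6.5 separately ends treatment for an adverse event that requires both drugs to be discontinued. Those rows are therefore not counted.

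The remaining wording is also soft. Section 7.2 is phrased as a recommendation. The neutrophil and platelet rows do not require a reduction but do not forbid one, and the anemia row is silent. The pre-syncope reduction depends on attribution, and the Table 8 restart depends on a benefit–risk judgment. This leaves room for an investigator to reduce anyway, but it does not say which instruction prevails. The explicit allowance for more conservative management, in a Table 9 footnote, covers PPE only.

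**Conclusion.** The concern holds for dose reductions. Six row pairs put Section 7.2 against Table 7 or Table 8 on the AR-42 dose even under the reading most favourable to the plan, and 12 do so if the rule is not applied per drug. The count treats each table row once and assumes that the pre-syncope is judged treatment-related and that treatment is restarted after the liver event. It says nothing about how often the pairs would occur; the documents give no basis for a frequency.

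A reader might also infer that the MTD or RP2D is compromised. The documents do not support that. The escalation rule in Table 3 counts DLTs and is untouched, and Section 6.7.4 sets no threshold on the frequency of dose modifications, so any effect on the RP2D is indirect. The point should be corrected because a stated rule, followed as written, cancels a reduction that another passage calls for, and the correction is cheap.

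**What to change.** Reconcile Section 7.2 with Tables 5 and 7–10 by stating two things:

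1. whether the highest-grade rule is applied separately to AR-42 and to pazopanib; and
2. whether the reduction instruction for a lower-grade toxicity still applies when a concurrent higher-grade toxicity carries no reduction.

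The test of the new text is that each of the 12 row pairs above leads to one instruction for each drug. Which instruction that is remains the sponsor's clinical decision.

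The cost is one or two sentences in Section 7.2 and the approval that Section 15.3 requires for any amendment. The sample size, the DLT definition, the escalation rule and the planned analyses do not change.

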7.3 Toxicity Grading

AEs will be characterized and graded according to NCI CTCAE v4.0.

7.4 General Instructions and Guidelines

- If treatment delays are required, the cycle may be extended to 5 weeks; however, all AR-42 doses must be taken during the first 4 weeks of the 5-week cycle. Any doses not given within the first 4 weeks of the extended cycle will be omitted.
- If one or both of the study medications are held due to toxicity, a **maximum of 3 consecutive weeks is permitted for recovery**. If recovery has not been sufficient to resume treatment 3 consecutive weeks after the decision to hold either or both of the study medications, both study medications must be discontinued.
- If AR-42 treatment must be interrupted for an AR-42-related toxicity, the patient should continue taking pazopanib unless dose modification instructions specifically indicate that pazopanib should be held or omitted.
- If pazopanib treatment must be interrupted due to a pazopanib-related toxicity, the patient should continue taking AR-42 unless dose modification instructions specifically indicate that AR-42 should be held or omitted..

7.5 AR-42 Dose Reduction Guidelines

7.5.1 Dose Reduction Steps for AR-42

AR-42 dose modifications, when required, will follow the predefined dose reduction steps outlined in Table 4.

Dose	Reduced AR-42 Dose*					
Reduction Step	When Starting Dose is 10 mg	When Starting Dose is 20 mg	When Starting Dose is 30 mg	When Starting Dose is 40 mg		
- 1	Discontinue AR-42	10 mg	20 mg	30 mg		
- 2		Discontinue AR-42	10 mg	20 mg		
- 3	Not Applicable	Not Applicable	Discontinue AR-42	10 mg		
- 4		Not Applicable	Not Applicable	Discontinue AR-42		
*The AR-42 dose indicated on this table should be taken according to the same instructions and schedule outlined in Section 6.2.1 .						

Table 4. AR-42 Dose Reduction Steps for Toxicity Management

7.5.2 Dose Modification Instructions for AR-42

In addition to the general dose modification instructions provided in Section 7.4, and the dose reduction steps listed on the table above, dose modification instructions for specific toxicities related to AR-42 are listed in Table 5.

Note: Some pazopanib-related toxicities may result in medical reasons to also hold, omit, or discontinue AR-42. When AR-42 modification/discontinuation is also required, the pazopanib dose modification tables (Table 7, Table 8, Table 9, and Table 10) will also specify the required AR-42 modification.

Grade (CTCAE v4.0)	AR-42 Modification (Refer to Table 4 for AR-42 dose reduction steps)
Blood and Lymphatic System Disorders	
Grade 3 or 4 anemia	Hold/omit ^A AR-42 until resolution to ≤ grade 2; transfusions are permitted.
Grade 3 or 4 febrile neutropenia	Hold/omit ^A until resolved; reduce dose by one dose reduction step when resuming treatment. ^B
Infections and Infestations	
Grade 3 infection	Hold/omit ^A until recovered to ≤ grade 2; at the investigator's discretion, the dose may be reduced by one dose reduction step when resuming treatment. ^B
Grade 4 infection	Hold/omit ^A until recovered to ≤ grade 2; reduce dose by one dose reduction step when resuming treatment. At the investigator's discretion, study treatment may be discontinued.
Investigations	
Grade 3 or 4 ECG QTc interval prolonged	Refer to Table 7 for instructions.
Grade 3 neutrophil count decreased; required ≤ 7 days for recovery to ≤ grade 2	Hold/omit ^A until ≤ grade 2. Dose reduction is not required when resuming treatment.
Grade 3 neutrophil count decreased; > 7 days required for recovery to \leq grade 2	Hold/omit ^A until ≤ grade 2; reduce dose by one dose reduction step when resuming treatment.
Grade 4 neutrophil count decreased	
Grade 3 platelet count decreased; ≤ 7 days required for recovery to ≤ grade 2	Hold/omit ^A until ≤ grade 2. Dose reduction is not required when resuming treatment.
Grade 3 platelet count decreased; > 7 days required for recovery to ≤ grade 2 Grade 4 platelet count decreased	Hold/omit [▲] until ≤ grade 2; reduce dose by one dose reduction step when resuming treatment.
Nervous System Disorders	
Grade 2 pre-syncope or grade 3 syncope (potentially reflecting cardiotoxicity)	Refer to Table 7 for instructions.
Other Toxicities Possibly Related to AR-42	(see footnote c)
Grade 2 toxicity that is persistent, intolerable, or unresponsive to optimal management	At the investigator's discretion, reduce AR-42 by one dose reduction step. ^B
Grade 3 toxicity	Hold/omit ^A until resolution to ≤ grade 1, baseline, or tolerable grade 2; reduce dose by one dose reduction step when resuming treatment. ^B
Grade 4 toxicity	Discontinue study treatment.
A. If recovery takes longer than the first 4 we	eks of the cycle, any remaining doses are omitted. DLT evaluation period [Section 6.7.1]), the dose may be

Table 5. AR-42 Dose Modification Instructions

B. At the investigator's discretion (after the DET evaluation period [Section 6.7.1]), the dose may be escalated to the most recent dose taken by the patient when treatment resumes.
C. Excludes alopecia, nausea and vomiting that improve with antiemetic therapy, lymphopenia, and other lab abnormalities that are asymptomatic and/or not clinically significant per investigator.

7.6 Pazopanib Dose Reduction Guidelines

Treatment with pazopanib will be interrupted and/or the dose reduced for clinically significant toxicities that are related to pazopanib therapy. Dose modifications will follow predefined dose reduction steps according to the guidelines shown on the table below.

Dose	Reduced Pazopanib Dose				
Reduction Step	When Starting Dose is 600 mg	When Starting Dose is 800 mg			
- 1	400 mg	600 mg			
- 2	200 mg 400 mg				
- 3	Discontinue pazopanib	200 mg			
- 4	Not Applicable Discontinue pazopanib				
*The pazopanib dose indicated on this table should be taken according to the same instructions and schedule outlined in Section 6.2.2 .					

 Table 6. Pazopanib Dose Reduction Steps for Toxicity Management

7.7 Pazopanib Dose Modification Instructions

In addition to the general dose modification instructions provided in Section 7.4, dose modification instructions for pazopanib-related toxicities are listed in Table 7, Table 8 (liver function abnormalities), Table 9 (PPE), and Table 10 (Other).

Note: For some toxicities, AR-42 instructions are also included on the tables listed above.

Toxicity	Pazopanib Modification			
	(Refer to Table 6 for pazopanib dose reduction steps)			
Cardiac	Hold/omit ^A pazopanib and determine LVEF.			
Grade 2 heart failure	 If < 15% absolute decline in LVEF compared with baseline or a decline in LVEF of < 10% compared with baseline and ≥ 50%: When symptoms of heart failure show clinical improvement, resume pazopanib with reduction in dose of one dose reduction step.^B If ≥ 15% absolute decline in LVEF compared with baseline or a decline in LVEF of ≥ 10% compared with baseline and < 50%: Continue holding until clinical improvement in symptoms and until LVEF improves to within 10% of baseline. Refer patient for cardiology consult. Reduce pazopanib dose by one dose reduction step when resuming treatment.^B At investigator's discretion, pazopanib may be discontinued. 			
Grade 3 or 4 heart failure	Discontinue pazopanib (also discontinue AR-42).			
Grade 3 or 4 MI	Discontinue pazopanib (also discontinue AR-42).			
Endocrine Disorders				
Grade 2 hypothyroidism	Continue pazopanib (dose reduction not required); initiate hypothyroidism management.			
Grade 3 or 4 hypothyroidism	Discontinue pazopanib; initiate/continue hypothyroidism management.			
Gastrointestinal Disorders				
≥ Grade 1 fistula	Discontinue pazopanib (also discontinue AR-42).			
≥ Grade 2 perforation				
Investigations				
Grade 3 ECG QTc interval prolonged See Section 6.8 for additional instructions regarding QT monitoring.	 Hold/omit^A pazopanib and AR-42. Check potassium, magnesium, and calcium levels; immediately administer potassium, magnesium, and/or calcium to achieve potassium level of ≥ 4 mEq, magnesium level of ≥ 2 mEq, and calcium WNL. Consider chronic supplementation for maintenance of electrolytes. Review with investigator prior to patient's next scheduled treatment, considering the following: Hold pazopanib and AR-42 until QTc recovers to pre-study treatment baseline (≤ grade 1 [≤ 480ms]). When QTc returns to baseline, resume pazopanib and AR-42 with additional QTc monitoring at earliest opportunity within 8 days after resuming study treatment. If QTc prolongation is thought to be related to pazopanib, decrease pazopanib and AR-42 doses by one dose reduction step when resuming study treatment. For recurrent grade 3 QTc thought to be related to pazopanib and AR-42. 			
Grade 4 ECG QTc interval prolonged	Discontinue pazopanib (also discontinue AR-42).			
Elevation in AST, ALT, and/or bilirubin	Refer to Table 8 .			

Table 7.	Pazopanib	Dose	Modification	Instructions
	i uzopullio	0000	mounounon	in ou douono

 ≥ Grade 2 Reversible Posterior Leukoencephalopathy Syndrome (RPLS) Grade 2 pre-syncope or grade 3 syncope (potentially reflecting cardiotoxicity) 	 An evaluation for RPLS should be performed if the patient presents with seizures, headache (in conjunction with other RPLS symptoms), visual disturbances, confusion, or altered mental function. If RPLS is diagnosed, discontinue pazopanib (also discontinue AR-42). Hold/omit^A pazopanib and AR-42. Obtain 12-lead ECG for cardiology review/consultation. Check potassium, magnesium, and calcium levels; immediately administer potassium, magnesium, and/or calcium to achieve potassium level of ≥ 4 mEq, magnesium level of ≥ 2 mEq, and calcium WNL. If ECG shows new dysrhythmia or QTc ≥ grade 2 (> 480ms), hospitalize for monitoring with cardiology consultation. Hold pazopanib and AR-42 until any potassium, magnesium, and
	 calcium abnormalities are corrected, symptoms resolved, and QTc improved to ≤ grade 1 (≤ 480ms). Reintroduce pazopanib and AR-42 with input from cardiology and with additional QTc evaluation, either concurrent with reintroduction or at earliest possible opportunity within 8 days from reintroduction. If event is thought to be related to study treatment, reduce the dose of pazopanib and AR-42 by one dose reduction step when resuming study treatment.^B Consider chronic supplementation for maintenance of electrolytes. For recurrent syncope or near-syncope thought to be related to study treatment, consider discontinuation of both pazopanib and AR-42.
Renal and Urinary Disorders	
≥ Grade 2 proteinuria	 Hold/omit^A pazopanib. If assessment of proteinuria was based on a urine dipstick reading, a 24-hour urine collection is required. Based on the 24-hour urine specimen: If grade 2 proteinuria, consult nephrology. If urine protein is < 3.0 gm/24 hours, study treatment may be continued without dose modification pending nephrology consult. If ≥ 3.0 gm/24 hours, hold study treatment until improvement to < 3.0 gm/24 hours or additional nephrology recommendations. If grade 3 proteinuria, consult nephrology and discontinue pazopanib.
Respiratory, Thoracic, and M	ediastinal Disorders
≥ Grade 2 pneumonitis	Discontinue pazopanib (also discontinue AR-42).
Skin and Subcutaneous Disc	rders
PPE (hand-foot syndrome)	See Table 9 for instructions related to PPE

Table 7. Pazopanib Dose Modification Instructions (continued)

Table 7. Pazopanib Dose Modification Instructions (continued)

Tuble III azopanie Beee mea	
Vascular Disorders	
Grade 3 hypertension defined as systolic BP >160 mmHg and diastolic BP >100 mm/Hg	 Hold/omit^A pazopanib until resolution to ≤ grade 2. Administer standard antihypertensive therapy. When resuming pazopanib, decrease pazopanib dose by one dose reduction step; monitor BP weekly for 4 weeks. If BP remains controlled for at least one cycle, the pazopanib dose may be escalated by one dose step at the investigator's discretion.
Grade 4 hypertension	Discontinue pazopanib (also discontinue AR-42)
	an the first 4 weeks of the cycle, any remaining doses for that cycle are 7.4 for additional information.

B. At the investigator's discretion (after the DLT evaluation period [Section 6.7.1]), the dose may be escalated by one dose step when the toxicity has resolved and treatment can be resumed.

